## 2.4. Determination of Sample Size

### Sample Size for FL

The study will test the null hypothesis that the IRRC-reviewed ORR is  $\leq 48\%$  against the alternative hypothesis that it is  $\geq 65.5\%$ . The sample size for the primary efficacy population for FL is estimated to be 91 subjects, with at least 90% power and 1-sided alpha = 0.025.

Safety analysis will be performed based on the Safety Population, with analysis focused on the IS FL subjects at the primary analysis database lock for FL submissions. With a total sample size of 120 FL subjects treated with ME-401 IS dosing regimen, if  $\leq 15$  subjects experience Grade  $\geq 3$  AESIs (i.e., subject incidence rate of  $\leq 12.5\%$  with 95% CI of 7.2–19.8%), the study can rule out the possibility of having an incidence rate  $\geq 20\%$  for Grade  $\geq 3$  AESIs with the IS dosing regimen. In addition, with a total sample size of 120 FL subjects, if  $\leq 5$  subjects experience a particular type of events (i.e., subject incidence rate of  $\leq 4.2\%$  with 95% CI 1.4–9.5%), the study can rule out the possibility of having an incidence rate of  $\geq 10\%$  for this AE.

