**Table 2: Most Common ( $\geq 20\%$ ) Adverse Events in the CS and IS Groups – Study ME-401-002 (N = 96)**

Preferred Term, n (%)	All Grades		Grade 3*	
	CS (N = 39)	IS (N = 57)	CS (N = 39)	IS (N = 57)
Diarrhea/colitis	19 (48.7)	21 (36.8)	10 (25.6)	4 (7.0)
Rash (all types)	15 (38.5)	8 (14.0)	4 (10.3)	1 (1.8)
Cough	14 (35.9)	9 (15.8)	0	0
Fatigue	12 (30.8)	14 (24.6)	1 (2.6)	0
Nausea	11 (28.2)	14 (24.6)	1 (2.6)	0
Decreased appetite	10 (25.6)	3 (5.3)	0	0
Pyrexia	9 (23.1)	5 (8.8)	1 (2.6)	0
Nasal congestion	9 (23.1)	5 (8.8)	0	0
Aspartate aminotransferase increased	8 (20.5)	11 (19.3)	2 (5.1)	0
Abdominal pain	8 (20.5)	8 (14.0)	0	0
Gastroesophageal reflux	8 (20.5)	4 (7.0)	0	0

Abbreviations: AEs = adverse events; CS = continuous schedule; IS = intermittent schedule; N = number of subjects; n = number of subjects in the category.

\* There were no Grade 4 or 5 AEs reported.

**Table 3: Grade 3\* Drug-Related Adverse Events of Special Interest (AESI) in the CS and IS Groups – Study ME-401-002 (N = 96)**

AESI, n (%)	CS Group (N = 39)	IS Group (N = 57)
Diarrhea/colitis	9 (23)	3 (5)
Rash, all types	3 (8)	0
AST/ALT increased	3 (8)	1 (2)
Mucositis	1 (3)	0
Pneumonia/pneumonitis	4 (10)	1 (2)

[figure not shown]
Abbreviations: AESI = adverse events of special interest; ALT = alanine aminotransferase; AST = aspartate aminotransferase; CS = continuous schedule; IS = intermittent schedule; N = number of subjects; n = number of subjects in the category.

\* There were no Grade 4 or 5 AEs reported.

It is hypothesized that delayed toxicities, such as diarrhea/colitis, rash, increases in transaminases, and pulmonary toxicities associated with PI3K $\delta$  inhibitors therapy might be due to an effect on regulatory T cells. To avoid such on-target side effects that are associated with continuous dosing schedules with other products in this class, the alternative option is to mitigate those toxicities by utilizing an intermittent dosing schedule. Preliminary data with ME-401 indicates that overall incidence of such events, especially clinically significant Grade 3 events, is lower in subjects treated with the IS. [Figure 4](#) represents time to adverse events of special interest (AESIs) in subjects treated in the CS and IS groups, with only 5 (9%) subjects who

experienced a related Grade 3 AESI compared to those in the CS group (16 [41%] subjects). This data indicates that the IS may significantly reduce a potential risk of developing immune-mediated adverse reactions.

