### 1.2. Timings of Analyses

The primary analysis for the primary efficacy endpoint of overall response rate (ORR) for the follicular lymphoma (FL) cohort (i.e., Primary Analysis for FL) will be triggered after all 91 subjects in the Primary Efficacy Population in FL (PEP FL) enrolled in the study (except those who discontinue early) have been followed for at least 6 months from the start of study drug.

The final analysis for DOR for follicular lymphoma (FL) to support the New Drug Application (NDA) initial filing for FL (i.e., NDA Analysis for FL) will be triggered after most responders in the Primary Efficacy Population have a minimum of 12 months of follow-up from first response.

The primary analysis for the primary efficacy endpoint of ORR for marginal zone lymphoma (MZL) (i.e., Primary Analysis for MZL) will be triggered after all subjects in the ITT MZL population enrolled in the study (except those who discontinue early) have been followed for at least 6 months from the start of study drug.

The final analysis for DOR for MZL to support the NDA filing for MZL (i.e., NDA Analysis for MZL) will be triggered after most responders in the ITT MZL population have a minimum of 12 months of DOR follow-up.

The final analysis includes all data collected through the time of the database lock. PK and Exposure-Response analyses will be performed by Nuventra, who will produce the analysis report.

An independent DSMB (Data Safety and Monitoring Board) will review descriptive summaries of accumulating safety, subject disposition, and limited efficacy data every 6 months. Further description of the DSMB analyses can be found in the DSMB charter.

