### **3.3.2. Incidence Rate of Adverse Event of Special Interests (AESIs)**

The rate of AESIs is calculated as the proportion of subjects with at least one AESI.

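### The statement that ≤15/120 Grade ≥3 AESIs excludes a 20% rate names no time horizon and assumes complete follow-up, which the FL primary lock requires only of the first 91 subjects

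*SAP*

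**What the plan says.** SAP 2.4 (Sample Size for FL) places the safety analysis on the Safety Population, "with analysis focused on the IS FL subjects at the primary analysis database lock for FL submissions". It continues: "With a total sample size of 120 FL subjects treated with ME-401 IS dosing regimen", "if $\leq 15$ subjects experience Grade $\geq 3$ AESIs" (12.5%, "with 95% CI of 7.2–19.8"%), "the study can rule out the possibility of having an incidence rate" of 20% or more. Protocol 11.1 carries the same text. A parallel statement says that 5 or fewer of 120 excludes 10% for a particular type of AE.

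Other parts of the plan bear on it:

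- **Lock trigger (SAP 1.2).** The FL primary analysis is triggered once the 91 PEP subjects "enrolled in the study (except those who discontinue early) have been followed for at least 6 months from the start of study drug". SAP 4.3 makes these the first 91 consecutive subjects of the ITT IS FL Population.
- **Who counts (SAP Table 4 and section 8).** All IS FL subjects in the Safety Population, not only the 91.
- **Estimator (SAP 3.3.2).** "The rate of AESIs is calculated as the proportion of subjects with at least one AESI".
- **Time-to-event analysis (SAP 8.3.4).** Kaplan-Meier time to first AESI and, as supportive, to first Grade ≥3 AESI. The listed outputs are the median with its CI, numbers of events and censored subjects, figures, and reverse Kaplan-Meier follow-up.
- **Later look (SAP Table 4).** Safety endpoints are summarised again at the NDA Analysis for FL.

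**The concern.** An exact binomial interval for 15/120 describes a single risk only if every subject was observed over the same period. At this lock, follow-up is guaranteed only for the 91. The remaining subjects enrolled later and have no minimum. A subject dosed shortly before the lock adds a full unit to the denominator while only part of that subject's risk has been observed. The bias runs in one direction, toward passing.

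Timing of onset matters too. Protocol 2.3 refers to late-appearing events with this drug class ("It is hypothesized that delayed toxicities, such as diarrhea/colitis, rash, increases in transaminases, and pulmonary toxicities"), and such events are the ones that short follow-up misses. Without a time horizon it is also unclear which rate of 20% is being excluded.

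At stake is a safety conclusion that readers of the submission may rely on. Following the plan as written, a 20% rate could be declared excluded partly because some subjects had not been observed long enough.

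**Working it through.** **Inputs.** From SAP 2.4: N = 120, cutoff 15, rate to exclude 20%, two-sided 95% interval (nominal 0.025 per side). From SAP 1.2 and 4.3: 91 subjects with 6 months required, leaving 120 − 91 = 29 with none required. (Protocol 8.3 reports 121 FL subjects enrolled on IS; I keep the planned 120.) Not in the documents, hence assumed: the follow-up of the 29, the onset pattern, a 6-month horizon for the 20%, and 6 months observed in all 91.

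**1. Reproduce the plan's figures (Clopper-Pearson).**
- 15/120: 7.17% to 19.78%. Matches 7.2–19.8%.
- 16/120: upper limit 20.7%, so 15 is the largest count whose upper limit is below 20%.
- 5/120: 1.4% to 9.5%. Matches.
- With all 120 observed for 6 months: P(Bin(120, 0.20) ≤ 15) = 0.0218, below 0.025.

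**2. Shorter follow-up in the 29.** Let f be the fraction of 6-month risk the 29 have shown by the lock. Then P(pass) = P(X₁ + X₂ ≤ 15), with X₁ ~ Bin(91, 0.20) and X₂ ~ Bin(29, 0.20f), by exact convolution.

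For constant hazard, 1 − exp(−6λ) = 0.20 gives λ = 0.0372 per month. If follow-up is uniform from a to 6 months, the mean risk is 1 − [exp(−λa) − exp(−6λ)] / [λ(6 − a)]:
- a = 3: 0.154 (f = 0.77)
- a = 0: 0.104 (f = 0.52)

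| Follow-up of the 29 at the lock | Risk in the 29 | P(≤15/120) | Multiple of 0.025 |
|---|---|---|---|
| All have 6 months (f = 1) | 0.200 | 0.022 | 0.9 |
| 90% of 6-month risk shown | 0.180 | 0.029 | 1.2 |
| Uniform 3–6 months, constant hazard | 0.154 | 0.042 | 1.7 |
| Uniform 0–6 months, constant hazard | 0.104 | 0.081 | 3.2 |
| No risk shown (f = 0) | 0 | 0.244 | 9.8 |

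In the 0–6 month case the expected crude rate is (91 × 0.20 + 29 × 0.104)/120 = 17.7%, although the true 6-month rate is 20%.

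**3. Onset pattern, with the 29 uniform over 0–6 months.**
- No events before month 2, constant hazard after: 0.121.
- Two-thirds of the 6-month risk in the first 2 months, linear within each part: 0.056.

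**4. The 5/120 statement (10% to exclude).** Error 0.016 with complete follow-up, and 0.042 if the 29 have shown half their risk.

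**5. Whether SAP 8.3.4 supplies the missing figure.** With about 12.5% of subjects having an event, the Kaplan-Meier median will very likely not be reached, so the median and its CI say nothing about 20%. Rates at fixed times with CIs are specified for DOR (3, 6, 9 and 12 months), PFS (6, 12, 18 and 24 months), TTF and OS (1 year), but not for AESIs.

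**The case against.** The case for leaving the text alone has real force.

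- **It is precision text, not a test.** It sits under sample size; SAP section 8 has no safety hypothesis or pass/fail criterion, and Protocol 11.2.2 says AESIs are summarised descriptively. This stands, and it limits the weight of the point. But the sentence states what the study can exclude, and a reader will take that as a conclusion.
- **The printed arithmetic is right.** It is.
- **Follow-up is handled elsewhere.** The Kaplan-Meier analyses censor event-free subjects (SAP 3.3.3), and safety is repeated at the NDA Analysis, when the later subjects will have more follow-up. Table 4 schedules only selected safety endpoints at the primary lock, and the Protocol synopsis gives 15/120 without mentioning that lock. All of this lessens the consequence. None of it is tied to the exclusion statement, which SAP 2.4 and Protocol 11.1 put directly after the reference to the primary lock.
- **Onset may be early rather than late.** The IS gives daily dosing for two cycles and intermittent dosing after that, and Protocol 2.3 presents the IS as a way to mitigate delayed toxicity. Early-weighted risk reduces the inflation (0.056 against 0.081 above) but does not remove it.

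A reader might also infer that only 91 subjects will have 6 months of follow-up at the lock. The documents do not say so. The trigger is a minimum, the lock may come later, and some of the 91 may have less because early discontinuations are excepted. If the other 29 all had at least 5 months, spread uniformly to 6, the error would be 0.027, about 1.1 times nominal.

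**Conclusion.** The point holds as a defect in how the exclusion is defined. The crude proportion, the absent horizon and a lock that guarantees follow-up for only 91 of 120 together bias the statement toward passing. For a true 6-month rate of 20%, with the 91 fully observed, the error runs from 0.022 to 0.244, about 1 to 10 times 0.025. Where the trial falls in that range depends on accrual timing and onset pattern, which the documents do not give. If a longer horizon was meant, the 91 would be incompletely observed as well and the error could be larger.

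Three stronger readings are not supported. No single inflation factor can be derived from the documents; each multiple above belongs to a stated scenario. The 15/120 statement is not the design's only quantitative safety claim, since SAP 2.4 also has 5/120 for FL and 25/184 and 9/184 for FL and MZL combined. And the plan does not ignore follow-up in its AESI analyses; it leaves the follow-up-adjusted analysis unconnected to the 20% statement and without a fixed-time rate.

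**What to change.** In SAP 2.4 and Protocol 11.1, state the target as the 6-month cumulative incidence of Grade ≥3 AESI on the IS. Then do one of the following:

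1. Add to SAP 8.3.4 the 6-month Kaplan-Meier or cumulative-incidence estimate with its 95% CI in all IS FL subjects, say which of the two is used, and base the 20% exclusion on its upper limit.
2. Keep the crude 15/120 statement, but make it only at a lock where every IS FL subject was dosed at least 6 months earlier. The NDA Analysis is a candidate, provided this condition is written down, because its own trigger refers to responders in the PEP only.

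Treat the 5/120 statement the same way.

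The cost is a change of wording and, under option 1, one added estimate per statement from data already collected. Visits and sample size are unaffected. The reported rate may be slightly higher and its interval slightly wider than the crude figures.

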### Sample Size for MZL

The study will test the null hypothesis that the IRRC-reviewed ORR is  $\leq 46\%$  against the alternative hypothesis that it is  $\geq 66.5\%$ . The sample size for the MZL population is estimated to be 64 subjects, with at least 90% power and 1-sided alpha = 0.025.

For the supplement submission for MZL indication, safety analysis will be focused on all subjects treated with ME-401 IS dosing regimen. With a total sample size of 184 subjects treated with the ME-401 IS dosing regimen in both the FL and MZL subjects, if  $\leq 25$  subjects experience Grade  $\geq 3$  AESIs (i.e., subject incidence rate of  $\leq 13.6\%$  with 95% CI of 9.0 – 19.4%), the study can rule out the possibility of having an incidence rate  $\geq 20\%$  for Grade  $\geq 3$  AESIs with the IS dosing regimen. In addition, with a total sample size of 184 subjects treated with the ME-401 dosing regimen in both the FL and MZL populations, if  $\leq 9$  subjects experience this type of adverse events (i.e., subject incidence rate of  $\leq 4.9\%$  with 95% CI 2.3–9.1%), the study can rule out the possibility of having an incidence rate of  $\geq 10\%$  for this AE.

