### **Sample Size for MZL**

Initially, the study was designed to test the null hypothesis that the IRRC-reviewed ORR is  $\leq 46\%$  against the alternative hypothesis that it is  $\geq 66.5\%$ . The sample size for the MZL population was estimated to be 64 subjects, with at least 90% power and 1-sided  $\alpha = 0.025$ . Enrollment in the MZL arm was closed by the Sponsor on 31 August 2022, with 32 of the 64 planned subjects enrolled. A sample of 32 subjects will provide preliminary data on the efficacy and safety of single agent zandelisib in relapsed/refractory MZL.

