### **8.3. Subject Enrollment**

As of this amendment, 121 subjects with FL and 32 subjects with MZL have been enrolled and treated with ME-401 on the IS. Enrollment in this study is now closed.

Subjects will be enrolled using an Interactive Web Response System (IWRS) process.

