### Sample Size for MZL

Initially, the study was designed to test the null hypothesis that the IRRC-reviewed ORR is  $\leq 46\%$  against the alternative hypothesis that it is  $\geq 66.5\%$ . The sample size for the MZL population was estimated to be 64 subjects, with at least 90% power and 1-sided alpha = 0.025.

The selection of a null hypothesis of 46% was based on a review of the ORR reported with therapies that have full or accelerated approval in the US for the treatment of relapsed MZL (single agent lenalidomide plus rituximab, [ibrutinib](#), [umbralisib](#)), adjusting for the requirement that subjects with MZL enrolled in the TIDAL study must have received  $\geq 2$  prior lines of therapy including an anti-CD20 antibody and chemotherapy. The selection of the alternative hypothesis was based on a clinically meaningful increase in the ORR by 20.5%.

Enrollment in the MZL arm was closed by the Sponsor on 31 August 2022, with 32 of the 64 planned subjects enrolled. The reason for early closure of enrollment is to focus enrollment of subjects with MZL in the global Phase 3 study ME-401-004. Early enrollment closure was communicated to all investigators in August 2022 and is being formalized in Amendment 5. A sample of 32 subjects will provide preliminary data on the efficacy and safety of single agent zandelisib in relapsed/refractory MZL.

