## REVISION HISTORY

Version #	Date (DD-MMM-YYYY)	Document Owner	Revision Summary
0.1	11-MAR-2019	[name]	Initial Release Version
0.2	05-APR-2019	[name]	Added revisions based on sponsor comments on v0.1 / 29MAR
1.0	18-APR-2019	[name]	Added revisions based on sponsor comments on v0.2 / 05APR
1.1	12-Jun-2020	[name]	Full version of SAP, update per protocol amendment 2
1.2	15-Jan-2021	[name]	Updated full version of SAP, based on protocol amendment 3 and sponsor's comments
2.0	12-Feb-2021	[name]	Final full version of SAP, based on sponsor's comments on v1.2
3.0	21-Jun-2021	[name]	Updated per Protocol Amendment 4

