**Table 4: Types of Analyses and Corresponding Populations for Planned Primary Analysis and NDA Analysis for FL**

Planned Analysis	Type of Analysis	Population	Analysis Set / Group
Primary Analysis for FL	Baseline disposition and demographics	ITT IS FL	ITT IS FL Total
	Primary endpoint ORR	PEP FL 	PEP FL
	Secondary endpoint DOR	PEP FL	DOR Primary Analysis Set for FL
	Selected Critical Secondary endpoints (PFS, OS)	PEP FL	PEP FL
	Selected Safety endpoints	Safety IS FL population	Safety IS FL Total
NDA Analysis for FL	Baseline disposition and demographics	ITT FL	PEP FL, ITT IS FL, ITT CS, ITT FL Total
	Primary endpoint ORR (Primary Analysis) and all secondary endpoints	PEP FL 	PEP FL
	Primary endpoint ORR (Supportive Analysis)	PEP FL 	PEP FL
	Primary endpoint ORR (Supportive Analysis)	ITT FL 	PEP FL, ITT IS FL, ITT CS, ITT FL Total
	Secondary endpoint DOR (Primary Analysis)	PEP FL	DOR Primary Analysis Set for FL
	Secondary endpoint DOR (Supportive Analysis)	ITT IS FL	DOR Supportive Analysis Set for FL
	Selected critical efficacy endpoints (PFS, OS, etc.)	ITT FL	PEP FL, ITT IS FL, ITT CS, ITT FL Total
Safety endpoints	Safety population	IS FL, IS MZL  , IS Total, CS	
Primary Analysis and NDA Analysis for MZL	Baseline disposition and demographics	ITT MZL	ITT MZL
	Primary endpoint ORR and all secondary endpoints (except DOR)	ITT MZL	ITT MZL
	Secondary endpoint DOR	ITT MZL	DOR Analysis Set for MZL
	Safety endpoints	Safety population	IS FL, IS MZL, IS Total, CS

 Primary analysis for ORR will include best response of PR and/or CR prior to first PD that is reported before the data cutoff date for FL Primary Analysis, among all patients in the Primary Efficacy Population in FL (PEP FL).

 Supportive analysis for ORR will include PR or CR achieved that is reported before the data cutoff date for NDA Analysis for FL, among all patients in the Primary Efficacy Population in FL.

 Supportive analysis for ORR will include PR or CR achieved that is reported before the data cutoff date for NDA Analysis for FL, among all patients in the ITT FL Population.

 Including MZL patients in the Safety Population who were dosed prior to the data cutoff date for the NDA Analysis for FL.

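### SAP v3.0 predates the closure of the MZL cohort: its 64-subject test, its safety counts for 184 subjects and its 6-month MZL response analysis no longer match the current protocol

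*SAP*

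**What the plan says.** **SAP.** The supplied version is 3.0, dated 21-Jun-2021; its revision history reads "Updated per Protocol Amendment 4".

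- Section 2.4 plans, in the present tense, a test of IRRC-reviewed ORR of at most 46% against at least 66.5% in MZL: "The sample size for the MZL population is estimated to be 64 subjects, with at least 90% power and 1-sided alpha = 0.025".
- The same section gives pooled safety thresholds: "With a total sample size of 184 subjects treated with the ME-401 IS dosing regimen in both the FL and MZL subjects", at most 25 subjects with a Grade 3 or higher AESI exclude a 20% rate, and at most 9 with a given AE exclude 10%. The matching rates are printed as 13.6% and 4.9%.
- Section 1.2 has two MZL analyses. The ORR analysis reads "i.e., Primary Analysis for MZL) will be triggered after all subjects in the ITT MZL population enrolled in the study" and requires at least 6 months from the start of study drug. A later DOR analysis needs most responders to have 12 months of DOR follow-up.
- Table 4 covers both in one block, "Primary Analysis and NDA Analysis for MZL".
- Section 4.3 limits the MZL DOR set to responses reported before the MZL Primary Analysis cutoff. Section 7.2.2 uses that set for both MZL analyses.

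**Protocol.**

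- The MZL sample size text, in the Synopsis and in 11.1, begins "Initially, the study was designed to test the null hypothesis that the IRRC-reviewed ORR is" at most 46%. It records closure on 31 August 2022 with 32 of 64 enrolled, to be formalised in Amendment 5, and concludes: "A sample of 32 subjects will provide preliminary data on the efficacy and safety of single agent zandelisib in relapsed/refractory MZL".
- Section 8.3 reports "121 subjects with FL and 32 subjects with MZL have been enrolled and treated with ME-401 on the IS".
- The Synopsis and sections 5.1, 7.2 and 11.2.2 describe one final MZL analysis of ORR and DOR together, projected in the Synopsis and 5.1 at about 14 months after the last subject's first dose.
- Section 11.2.1 nevertheless fixes the MZL DOR set at the cutoff of an MZL primary analysis, which the protocol's timing text never defines.

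**The concern.** The two documents describe different MZL plans. The SAP promises a powered test in a cohort twice the size of the one enrolled, and a reader of the SAP alone would take 90% power as the basis for the MZL result. Its pooled safety counts presuppose 184 subjects, a total that cannot now be reached because enrollment is closed.

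The timing difference is the part that could change a reported number. Protocol 11.2.1 leaves population detail to the SAP, and under SAP 1.2 the MZL primary analysis is the 6-month one. Under the protocol's timing text the only available cutoff is that of the final analysis. Two programmers working from these texts could build different DOR denominators. A subject whose first response is reported after the 6-month cutoff would count in the protocol's final ORR but be missing from the DOR set.

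**Working it through.** **1. MZL test.** Inputs: null 46%, alternative 66.5%, one-sided alpha 0.025 and n = 64 (SAP 2.4); n = 32 (Protocol 8.3 and 11.1). Method: exact one-sample binomial. Take the smallest r with P(X ≥ r | n, 0.46) ≤ 0.025; power is P(X ≥ r | n, 0.665).

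- n = 64, the plan's own figure: r = 38 (59.4%), alpha 0.0217, power 0.908. The SAP's statement reproduces.
- n = 32: r = 21 (65.6%), alpha 0.0201, power 0.622. With r = 20 alpha would be 0.0451, so 21 is the minimum.
- Precision at an observed 50%, Clopper-Pearson 95%: 16/32 gives 31.9–68.1% (half-width 18.1 points); 32/64 gives 37.2–62.8% (12.8 points).

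**2. Pooled safety counts.** The SAP total is 120 + 64 = 184. The treated intermittent-schedule total is 121 + 32 = 153 (Protocol 8.3). The Clopper-Pearson upper limit is the 0.975 quantile of Beta(x + 1, N − x).

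| Events / N | 95% CI | Threshold | Excluded? |
|---|---|---|---|
| 25/184 (SAP) | 9.0–19.4% | 20% | yes, as printed |
| 9/184 (SAP) | 2.3–9.1% | 10% | yes, as printed |
| 25/153 | 10.9–23.2% | 20% | no |
| 9/153 | 2.7–10.9% | 10% | no |
| 20/153 | 8.2–19.5% | 20% | yes |
| 21/153 | 8.7–20.2% | 20% | no |
| 7/153 | 1.9–9.2% | 10% | yes |
| 8/153 | 2.3–10.04% | 10% | no |

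Read as rates, the thresholds survive: 0.136 × 153 = 20.8 allows 20 events, and 0.049 × 153 = 7.5 allows 7. Only the counts fail. With the planned figure of about 120 FL, N = 152 and the maximum counts are still 20 and 7. The FL-only thresholds are unaffected at 121: 15/121 gives 7.1–19.6% and 5/121 gives 1.4–9.4%.

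**3. Cutoffs.** Scheduled scans fall on days 61, 121, 182, 274, 365 and 456 (Protocol Appendix 1). With 30.4375 days per month, for the last subject enrolled:

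- 6 months: 6 × 30.4375 = 183 days, so 3 scheduled scans.
- 14 months: 14 × 30.4375 = 426 days, so 5 scheduled scans.

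Responses first seen at day 274 or 365 in that subject fall between the two cutoffs. Earlier-enrolled subjects have more scans by either cutoff.

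The number affected can only be illustrated. Protocol 1.6.2.4 reports 48 of 54 Phase 1b responders (89%) responding at the assessment after 2 cycles. Those were FL and CLL/SLL subjects, so applying this to MZL is an assumption. At the SAP's alternative, 0.665 × 32 gives about 21 responders, and 6/54 = 11% of 21 is about 2 responding after the first scan. The day-121 and day-182 scans would catch some of these, leaving perhaps 0 to 2 subjects.

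**The case against.** The strongest reply is that this is version lag. A SAP dated June 2021 could not contain a closure made in August 2022, and a later SAP may exist. That stands, and the point is therefore limited to the supplied version. It does not remove the undefined MZL primary analysis in Protocol 11.2.1, which is in the current protocol.

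Several stronger readings are tempting, and the documents do not support them:

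- *The SAP miscalculated.* It did not; its power and both intervals reproduce.
- *The trial will run an MZL test at 62% power.* The protocol places that test in the past, and SAP 7.1 gives no MZL p-value or success rule. The 62.2% shows how far the stated power is from the enrolled cohort and nothing more.
- *The safety conclusions are wrong.* The counts are tied explicitly to 184, no text carries them to 153, and the printed rates would still hold.
- *Table 4 also separates a 6-month ORR from a later DOR.* It is one combined block in which ORR also belongs to the later analysis. Only SAP 1.2 sets the 6-month timing.
- *SAP 10, which declares no changes from the protocol, is false.* Amendment 4 is not available to test it against, and it becomes true once the SAP is aligned.
- *The study-duration minimum of 6 months in SAP 2.3, and the differing triggers in Protocol 7.2 and 11.2.2, are conflicts.* Fourteen months satisfies the minimum. The two triggers are bridged in the Synopsis and 5.1: (426 − 61)/30.4375 = 12.0 months after a first response at day 61.

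Fixing a DOR set at a primary cutoff and following it longer is also the declared FL design, so that structure is not a fault in itself. The fault is that the MZL cutoff means different things in the two documents.

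**Conclusion.** The mismatch is real and should be fixed. The stated MZL size and power (64, at least 90%) are not those of the enrolled cohort (32, and 62.2% for the same test). The counts of 25 and 9 would no longer exclude 20% and 10% at 153 subjects. SAP 1.2 contains an MZL analysis absent from the protocol, and this leaves membership of the MZL DOR set ambiguous.

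The consequence is limited. No MZL decision rule and no FL result changes, and the DOR ambiguity probably touches few subjects, on the assumption that MZL responses come as early as the Phase 1b responses did. The conclusion also assumes that v3.0 is the operative SAP. If a later version exists, it should be checked for the same items.

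**What to change.** Before MZL database lock:

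- **SAP 2.4:** replace the MZL test and power statement with estimation in 32 subjects using an exact 95% CI (for example 31.9–68.1% at 16/32). Restate the pooled counts as at most 20 of 153 (CI 8.2–19.5%) and at most 7 of 153 (CI 1.9–9.2%), or delete them.
- **SAP 1.2:** replace the 6-month MZL ORR analysis with the protocol's single final ORR and DOR analysis, and relabel the MZL block of Table 4 to match.
- **Protocol 11.2.1 and SAP 4.3:** define the MZL DOR set by that final cutoff, and carry this into SAP 7.2.2.

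SAP 10 needs no edit once this is done. Harmonising the wording of SAP 2.3 and of the Protocol 7.2 trigger is optional.

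The cost is a SAP amendment and a short protocol clarification, with no new subjects or data. What is given up is the stated 90% MZL power and the counts for 184.
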